7. INVESTIGATIONAL PLAN

7.1. Overall Study Design

This is a Phase 3b, double-blind, randomized, placebo-controlled, multicenter study. Eligible subjects will have a diagnosis of PBC with bilirubin levels of $>ULN$ and $\leq 3 \times ULN$ or ALP $>5 \times ULN$. Subjects enrolled will be at higher risk of liver-related clinical complications.

Approximately 350 subjects meeting all enrollment criteria will be recruited into the study over an approximate 2-year period, randomly allocated to treatment with either OCA or matching placebo in a 1:1 ratio (Figure 1). Subjects will be screened during a 1 to 8-week Screening period prior to entering the study to allow for the collection of repeat serum chemistry samples (at least 2 weeks apart) to confirm pretreatment ALP and total bilirubin values (refer to [Section 9.7.6](#)). Randomization will be stratified by UDCA treatment (yes/no) and baseline bilirubin categories ($>ULN/\leq ULN$). In addition to the placebo control arm, multiple historical control groups (concurrent and retrospective) will be used.

Investigational product will be taken orally, once daily. Subjects who are non-cirrhotic or classified as Child-Pugh A at Screening will initiate investigational product once daily with 5-mg OCA or matching placebo. Following 3 months of once daily treatment with investigational product, the dose should be titrated to a maximum 10 mg OCA or matching placebo once daily, based on tolerability (see [Section 7.3](#)).

[figure not shown]
Subjects with cirrhosis (see [Section 9.7.3](#)) and classified as Child-Pugh Class B or Child-Pugh Class C will follow a modified dosing regimen, and will initiate investigational product once weekly with the 5-mg OCA or matching placebo dose. In addition, these subjects will follow a modified titration plan, which is outlined in [Appendix A](#).

It is anticipated that subjects will be followed for a minimum of approximately 6 years. The study will continue until approximately 121 adjudicated primary endpoint events have been accrued in unique subjects, or until the Sponsor (eg, based on advisement by the Data Monitoring Committee; DMC) terminates the study.

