13.1.1.1. Comparability of Historical Controls

Utilization of both historical control/observational databases (UK-PBC and Global PBC Study Group), with more than 6000 subjects each, allow for a rigorous subject level meta-analysis. The historical databases include long-term follow up, detailed subject-level information such as

baseline clinical characteristics, longitudinal liver biochemistry, and long-term outcomes, and span a broad range of subject characteristics that may influence disease (disease state, age, gender, and regional differences in standard of care). Historical controls from both databases will be chosen based on the same study inclusion/exclusion criteria where possible.

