13.1.2. Determination of Sample Size

The following assumptions were used in sample size calculations:

- Exponential survival curves, placebo survival estimate of 0.5 at 8 years with a hazard ratio of 0.60, and total study duration of 8 years, allowing for 2 years accrual and 6 years of follow up.
- Subjects will be randomized in a 1:1 ratio to placebo or OCA.
- The 2 groups will be compared using a 2-sided log rank test at the 5% level of significance.

Based on the randomization ratio, significance level, and assumed hazard ratio, a total of 121 events (both groups combined) will provide 80% power to demonstrate a statistically significant difference between OCA and placebo on time to liver-related outcomes, including all-cause mortality.

In addition, based on the remaining assumptions stated above, it is estimated that approximately 350 subjects will be enrolled to attain 121 events.

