Propensity scores will be estimated using the available covariates that predict receiving the treatment. Only covariates and not outcome variables will be included in the propensity score estimation. Therefore, there is no chance of biasing results in favor of one treatment.

The covariates and factors collected in the historical databases will be specified in the SAP.

Propensity scores will be estimated first through a logistic regression model with treatment group as the dependent variable and the above covariates/factors as independent variables. Then the stratum boundaries are determined based on the propensity score values for both groups (OCA population and control [historical and randomized placebo]) combined or in the OCA population or historical control group alone. Based on recommendations in the literature, quintiles of the estimated propensity score from the combined group will be used to determine the stratum boundary cut-offs for the different strata.

Outcome events collected in the historical database are: death (liver-related and all-cause), liver transplant, hepatocellular carcinoma, and other. Other is defined as cirrhosis or decompensation such as ascites, variceal bleed, and encephalopathy.

The propensity score quintile will be then be used as the stratification factor in the stratified log rank test to compare randomized OCA-treated subjects in the ITT population and historical controls (Overall Historical Control Population: both the UK-PBC Group and Global PBC Study Group databases) on the following outcomes:

- Time to death (all-cause)
- Time to liver-related death
- Time to liver transplant
- Time to liver transplant or death (all-cause)

- Time to liver transplant or liver-related death
- Time to hepatocellular carcinoma

KM estimates of the distribution of the time-to-event will be tabulated and graphed by treatment group. The tabulation will include the KM estimate of the medians and corresponding 95% CIs if the medians can be estimated. The number and percent of subjects censored and with events will be presented. The hazard ratio and 95% CI will be determined based on a Cox regression model stratified by randomization strata to estimate the magnitude of the effect.

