13.1.9. Alternative Primary Analysis

Based on sample size re-estimations, it may be determined that subjects will be enrolled to receive open-label OCA from that point forward, and the new primary efficacy analysis will become the comparison of all subjects in OCA population, to all control subjects (randomized placebo and historical controls) on time to liver transplant or death (all-cause) (see [Section 13.1.2.1](#)). Similar statistical methodology as specified above in [Section 13.1.8](#) for supportive analyses will be utilized.

The propensity score quintile will be then be used as the stratification factor in the stratified log rank test to compare groups. KM estimates of the distribution of the time-to-event will be tabulated and graphed by treatment group. The tabulation will include the KM estimate of the medians and corresponding 95% CIs if the medians can be estimated. The number and percent of subjects censored and with events will be presented. The hazard ratio and 95% CI will be determined based on a Cox regression model stratified by randomization strata to estimate the magnitude of the effect.

In addition, the outcome events specified above in Section 13.1.8 will also be evaluated to compare all subjects in OCA population to all control subjects (randomized placebo and historical controls).

Sensitivity analyses will be conducted limiting to the separate individual historical control databases, ie, UK-PBC Group and Global PBC Study Group. To evaluate the robustness of the propensity score estimations, additional algorithms and factors may be considered.

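### Propensity strata cut at combined-sample quintiles can leave confounding in the OCA-versus-historical tests when the control pool is large and differs from the trial population

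*Protocol*

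**What the plan says.** Section 13.1.8 names three possible bases for the stratum boundaries: both groups combined, the OCA population alone, or the historical controls alone. It then chooses the first: "quintiles of the estimated propensity score from the combined group will be used to determine the stratum boundary cut-offs for the different strata". The resulting quintile stratifies the log-rank test for six OCA-versus-historical outcomes.

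Section 13.1.9 applies the same device to the alternative primary analysis of transplant or death, in which the controls are randomized placebo and historical subjects together: "The propensity score quintile will be then be used as the stratification factor in the stratified log rank test to compare groups".

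In both sections the hazard ratio and its interval come from a Cox model stratified by the randomization strata, not by the propensity strata.

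Because only covariates, and no outcomes, enter the score, 13.1.8 concludes: "Therefore, there is no chance of biasing results in favor of one treatment".

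The covariate list is left to the SAP; the boundary rule is not. Other algorithms are mentioned only as something that may be considered.

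On the control pool, 13.1.1.1 describes two registries "with more than 6000 subjects each", with the trial's entry criteria applied to them as far as the data allow. Section 13.1.1 adds that each historical population must be shown to be comparable with the randomized subjects. The number selected and the expected overlap are not given.

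**The concern.** The test is meant to ask whether OCA changes the hazard given the covariates. It can do so only if OCA and control subjects within a stratum carry similar risk. When controls far outnumber OCA subjects, combined quintiles are nearly the controls' own quintiles. If the trial population is shifted on the score, a large share of OCA subjects falls into one open-ended end stratum. Controls in that stratum sit mainly near its inner edge and OCA subjects further out, so the comparison is confounded even if every covariate was measured.

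At stake are all six supportive outcomes, and the trial's primary test if the open-label switch in 13.1.2.1 is used. The sentence denying any chance of bias would also stand in the protocol as a justification that does not follow. Leaving outcomes out of the score prevents the score from being tuned to the result. It does not remove confounding within coarse strata, or from covariates that were not recorded.

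**Working it through.** **Inputs from the protocol (13.1.2).** "The 2 groups will be compared using a 2-sided log rank test at the 5% level of significance"; "placebo survival estimate of 0.5 at 8 years with a hazard ratio of 0.60"; "allowing for 2 years accrual and 6 years of follow up". As a check on these, the Schoenfeld event count is 4 × (1.960 + 0.842)² / (ln 0.60)² = 31.40 / 0.2609 = 120.3, so 121, as the protocol states. With 350 subjects randomized 1:1, the OCA arm is 350 / 2 = 175.

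**Inputs assumed, because the protocol does not give them.** Selected pool of 175 to 12,000; score normal with SD 1 in each group; mean shift d between trial and registry; hazard ratio about 2 per SD of score; for the power runs, a transplant-or-death hazard of 0.04 per year at the trial mean and 6 to 8 years of follow-up.

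**Step 1: crowding.** With a very large pool the top cut-off is the controls' 80th percentile, 0.84 SD above their mean. The share of OCA subjects above it is 1 − Φ(0.84 − d): 0.37 at d = 0.5, 0.56 at d = 1 and about 0.75 at d = 1.5. Simulation agrees (share of OCA subjects in the top stratum):

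| Pool | d = 0.5 | d = 1 | d = 1.5 |
|---|---|---|---|
| 175 | 27% | 33% | 37% |
| 1000 | 33% | 48% | 63% |
| 3000 | 36% | 54% | 71% |
| 12,000 | 36% | 56% | 74% |

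**Step 2: what the strata leave behind.** Up to d = 0.5, combined quintiles leave 11% to 12% of the raw score difference whatever the pool, about the same as OCA quintiles. With 12,000 controls this rises to 18% at d = 1 and 36% at d = 2. With 175 controls it stays near 10%.

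**Step 3: effect on the test, trial sicker.** Planned rule against OCA deciles with controls trimmed to the OCA score range. Ranges show the spread between repeat simulations; at 600 replicates the standard error of a 5% rate is √(0.05 × 0.95 / 600) = 0.9 points.

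| Controls, shift | Null rejection: planned | Null rejection: alternative | Power at 0.60: planned | Power at 0.60: alternative |
|---|---|---|---|---|
| 1000, 1 SD | 11–15% | 4.5–6% | 42–47% | 63–67% |
| 3000, 1 SD | 17–19% | 6% | 43% | 75% |
| 3000, 1.5 SD | 48–50% | 4–6% | 13% | 68–69% |
| 1000, 0 SD | – | – | 80% | 79% |
| 3000, 0 SD | – | – | 82% | 82% |

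At 0.5 SD the planned rule rejects a true null about 7% to 8% of the time and loses about 5 to 10 points of power.

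**Step 4: direction.** With a sicker trial population and a shift of 1 to 1.5 SD, null rejection in favour of OCA is 0 to 0.5%, below the nominal 2.5%; the excess is against OCA. With a trial population healthier by 1.5 SD, null rejection under the planned rule is about 6% to 18%, mostly in favour of OCA.

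**Step 5: which change produces the gain.** At 1000 controls and 1 SD (null rejection, power):

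- combined quintiles: 15%, 42%
- combined deciles: 8%, 57%
- OCA quintiles: 8%, 57%
- OCA deciles with trimming: 6%, 63%

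At 3000 controls and 1.5 SD, combined deciles still reject 18% of the time and OCA quintiles 7%. OCA quintiles without trimming can do worse than the planned rule: with 1000 controls and a trial population healthier by 1.5 SD they reject 19% of the time, against 9%.

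**The case against.** The strongest reply is that the crowding may never occur. The figure of more than 6000 per registry is the size before selection. Controls must meet the trial's entry criteria where the data permit and must be shown to be comparable. The statement "Subjects enrolled will be at higher risk of liver-related clinical complications" follows from the bilirubin and ALP entry criteria, which look applicable to registries that hold longitudinal liver biochemistry. So it does not show that trial subjects differ from the controls finally chosen. This stands: a reader might infer from the registry sizes that OCA subjects will crowd into one or two strata, and the documents do not support that as a fact.

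It does not remove the point. The comparability condition carries no numerical criterion in the protocol and does not alter the boundary rule. A propensity score also adds up small differences: six independent covariates, each 0.4 SD apart, give √6 × 0.4 = 0.98 SD.

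Three further limits stand. The high null rejection rates should not be read as false efficacy claims, since with a sicker trial population they run against OCA. The gain cannot be credited to the boundary alone, because finer strata and trimming share it. And the planned primary analysis, randomized OCA against randomized placebo, does not use these strata; a change in treatment allocation would itself require a protocol amendment.

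**Conclusion.** The concern holds conditionally. The protocol fixes a rule that performs well when the groups overlap, or when the selected pool is near the size of the OCA arm, and badly when the pool is large and the shift is about 1 SD or more. Under the stated assumptions (score hazard ratio 2 per SD, 1000 to 3000 controls, trial population sicker by 1 to 1.5 SD), null rejection is about 13% to 50%, almost all against OCA, and power is about 13% to 45%. The alternative gives about 5% to 8% and 50% to 77%. The likely harm in that setting is a real benefit hidden, or a misleading unfavourable result. A healthier trial population would reverse the direction.

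Pool size, separation and prognostic strength are assumptions, so no single figure here predicts what this trial will see. Two points do not depend on them. The statement that bias is impossible is wrong as written, and the reported hazard ratio comes from strata other than those used in the test. Since overlap is unknown when the rule is set, a rule that is robust to it is preferable.

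**What to change.** In 13.1.8, and by reference in 13.1.9:

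- Restrict controls to those whose propensity score lies within the OCA range, and cut the strata at the deciles of the OCA score. OCA quintiles without trimming are not enough.
- Keep combined-group quintiles as a sensitivity analysis.
- Stratify the accompanying Cox model by the same propensity strata, so that the test and the hazard ratio address the same comparison.
- Replace the sentence denying any chance of bias with a statement that excluding outcomes from the score does not remove residual or unmeasured confounding.

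The cost is a wording change carried into the SAP, which section 13 already requires before propensity scores are determined. No new data or subjects are needed. Registry controls with no comparable OCA subject are dropped; in the simulations this cost no detectable power when the groups were already balanced.

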13.1.9. Alternative Primary Analysis

Based on sample size re-estimations, it may be determined that subjects will be enrolled to receive open-label OCA from that point forward, and the new primary efficacy analysis will become the comparison of all subjects in OCA population, to all control subjects (randomized placebo and historical controls) on time to liver transplant or death (all-cause) (see [Section 13.1.2.1](#)). Similar statistical methodology as specified above in [Section 13.1.8](#) for supportive analyses will be utilized.

The propensity score quintile will be then be used as the stratification factor in the stratified log rank test to compare groups. KM estimates of the distribution of the time-to-event will be tabulated and graphed by treatment group. The tabulation will include the KM estimate of the medians and corresponding 95% CIs if the medians can be estimated. The number and percent of subjects censored and with events will be presented. The hazard ratio and 95% CI will be determined based on a Cox regression model stratified by randomization strata to estimate the magnitude of the effect.

In addition, the outcome events specified above in Section 13.1.8 will also be evaluated to compare all subjects in OCA population to all control subjects (randomized placebo and historical controls).

Sensitivity analyses will be conducted limiting to the separate individual historical control databases, ie, UK-PBC Group and Global PBC Study Group. To evaluate the robustness of the propensity score estimations, additional algorithms and factors may be considered.

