5.5.2.3. Rationale for Control Groups

Placebo Control Group

The use of a randomized placebo control group added to established standard of care provides the best scientific evidence of efficacy and safety. The use of a placebo control provides a concurrent comparator group, accounting for not only a placebo effect but a standard of care effect. Notably, accounting for the standard of care effect is critical when designing an outcome-based study conducted globally when there are regional differences in the treatment of subjects with PBC.

Historical Control Group

The available robust historical PBC observational datasets (UK-PBC and Global PBC Study Group) will also be leveraged to provide further comparative evaluation of the clinical benefit of OCA. Each database includes >6000 patients with long-term follow-up.

Comparison of OCA treatment to the historical controls may provide utility in addressing potential bias or confounds associated with the placebo arm. For example, bias associated with the potential addition of commercial OCA and/or differences in long-term standard of care between the treatment arms including ancillary treatments and diagnostics.

Therefore, further evaluation of the effect of OCA will compare OCA treatment versus historical controls, and will be supportive to placebo comparisons (ie, comparisons to historical and placebo controls will be evaluated separately).

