13.1. Efficacy Analysis

13.1.1. Analysis Populations

The following subject populations will be evaluated and used for presentation and analysis of the data:

- The Randomized Population will include all randomized subjects.
- The Intent-to-Treat (ITT) Population will include all randomized subjects who receive any amount of investigational product (OCA or placebo). The ITT Population will be the primary population used for efficacy analyses. Treatment assignment will be based on the randomized treatment.
- The Safety Population will include all subjects who received any amount of investigational product (placebo or OCA). The Safety Population will be the primary population used for safety analyses. Treatment assignment will be based on the treatment actually received.
- The PK population will include all OCA subjects who have at least one confirmed fasted analyzable sample. Subjects must have been fasting for approximately 8 hours prior to the visit and must not have any major protocol deviations that potentially affect exposure levels. The PK population will be used for OCA PK analyses.
- The Overall Historical Control Population will include subjects from the United Kingdom (UK) -PBC Group and Global PBC Study Group databases with demonstrated comparability to randomized subjects in this clinical study (747-302) with respect to both subject characteristics and disease progression.
- The UK-PBC Historical Control Population will include subjects from the UK-PBC Group databases with demonstrated comparability to randomized subjects in this clinical study (747-302) with respect to both subject characteristics and disease progression.
- The Global PBC Historical Control Population will include subjects from the Global PBC Study Group database with demonstrated comparability to randomized subjects in this clinical study (747-302) with respect to both subject characteristics and disease progression.

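### If the open-label switch is used, Section 13.1.9 replaces the randomized primary comparison with a pooled placebo-plus-registry control and keeps no randomized-only analysis

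*Protocol*

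**What the plan says.** Section 13.1.3 sets the primary analysis as randomized OCA against randomized placebo on the composite endpoint. Section 13.1.2.1 adds a contingency. If, after 4 years of accrual, at least 2 more years are needed to randomize enough subjects for 121 adjudicated events, everyone enrolled from then on receives open-label OCA. Those already randomized continue blinded on their allocated treatment.

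Section 13.1.9 says what happens to the analysis in that case: "the new primary efficacy analysis will become the comparison of all subjects in OCA population, to all control subjects (randomized placebo and historical controls", with transplant or all-cause death as the endpoint and a log-rank test stratified by propensity-score quintile. The sensitivity analyses it commits to restrict the historical controls to one registry or the other, and it allows further propensity algorithms and factors. None of these isolates the randomized subjects.

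Section 5.5.2.3 describes the role of the registries differently. The historical comparison is supportive, and "comparisons to historical and placebo controls will be evaluated separately".

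All three historical control populations in Section 13.1.1 consist of registry subjects "with demonstrated comparability to randomized subjects in this clinical study (747-302) with respect to both subject characteristics and disease progression". Section 13.1.8 notes that outcome variables stay out of the propensity model and concludes: "Therefore, there is no chance of biasing results in favor of one treatment".

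**The concern.** The randomized comparison protects the primary conclusion from confounding. The switch does not destroy it, because the randomized subjects remain blinded and in follow-up, but 13.1.9 stops using it. The replacement mixes randomized and open-label OCA on one side, and randomized placebo and registry patients on the other. Each registry holds more than 6,000 patients, so after selection the registries could easily outnumber the placebo arm. The test would then be mainly trial against registry. Any prognostic difference that the propensity score fails to capture would pass into the primary result.

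The selection rule for controls adds a second problem. Section 13.1.1 names disease progression separately from subject characteristics and takes randomized subjects of both arms as the reference. If progression means course during follow-up, registry patients are admitted on something close to the outcome. Keeping outcomes out of the propensity model does not address how controls were admitted in the first place.

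**Working it through.** **The plan's own figure.** Inputs from Section 13.1.2: "The 2 groups will be compared using a 2-sided log rank test at the 5% level of significance"; "placebo survival estimate of 0.5 at 8 years with a hazard ratio of 0.60, and total study duration of 8 years"; "Subjects will be randomized in a 1:1 ratio to placebo or OCA". Schoenfeld's formula gives 4 × (1.960 + 0.842)² / (ln 0.60)² = 4 × 7.85 / 0.2609 = 120.3, so 121 events. The stated 121 events for 80% power is reproduced (80.2%).

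**Sections 5.5.2.3 and 13.1.9 side by side.**
- Role of registry controls: supportive in 5.5.2.3; part of the primary control group in 13.1.9.
- Relation to placebo: separate in 5.5.2.3; pooled in 13.1.9.
- Exception for the switch in 5.5.2.3: none stated.
- Randomized-only analysis after the switch: none named in 13.1.9.

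**Illustration of what pooling does to the type I error.** The Protocol does not give the number of registry patients left after selection, the number of open-label subjects or the events expected on transplant or death. All the following are therefore assumptions:
- 175 placebo subjects (half of the planned 350);
- 275 OCA subjects (175 randomized plus 100 open-label);
- 1,000 registry controls (range 500 to 2,000);
- 50 to 80 OCA events, with the same event proportion among controls;
- no true OCA effect, and a registry hazard 20% above the trial's after adjustment.

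Steps:
1. Registry share of controls: w = 1000/1175 = 0.851.
2. Bias in the log hazard ratio: b = 0.851 × ln 1.2 = 0.851 × 0.1823 = 0.155.
3. Control events: 50 × 1175/275 = 214, and 80 × 1175/275 = 342.
4. Standard errors: √(1/50 + 1/214) = 0.157, and √(1/80 + 1/342) = 0.124.
5. Shift b/SE: 0.99 and 1.25.
6. Two-sided type I error, Φ(−1.96 + b/SE) + Φ(−1.96 − b/SE): 16.7% and 23.9%.

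Over 500 to 2,000 registry controls the result is 13% to 29%. A residual difference of 10% gives 7% to 11%. With 175 OCA subjects instead of 275 and 1,000 registry controls, the 20% case gives 18% to 25%, so the result does not depend on the open-label number.

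**Cross-check by simulation.** This used an unstratified log-rank test, 2,000 runs per setting, 175 OCA, 175 placebo and 1,000 registry subjects, censoring at 6 to 8 years and no OCA effect. At a residual registry hazard ratio of 1.25, significance in favour of OCA occurred in 19% of runs (8-year control survival 0.75) and 36% (survival 0.50), against a nominal 2.5%. At a ratio of 1.0 it was about 2%. At 0.8 the error ran against OCA (two-sided 21% and 35%). With no registry controls the two-sided rate was 4.9% to 5.0%.

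**Power if the randomized test stays primary.** With HR 0.60 on the composite, power = Φ(√d/2 × 0.511 − 1.96): 80.2% at 121 events, 72.4% at 100 and 62.7% at 80.

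**The case against.** **An exception rather than a conflict.** Section 5.5.2.3 can be read as describing the base design, with 13.1.9 as an express alternative reached only after a blinded trigger. Section 13.1.2.1 also requires a protocol amendment for changes to treatment allocation. This softens the conflict but does not remove it: 5.5.2.3 states no exception, and the amendment requirement does not alter the analysis already fixed in 13.1.9. A reader might also infer that the switch itself inflates the type I error. The documents do not support that, because the trigger uses pooled, blinded event counts.

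**Contamination by commercial OCA.** Section 5.5.2.3 gives this as a reason to consult the registries. The reason is fair, but that section still concludes that they are supportive. Pooling leaves the affected placebo subjects in the control group.

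**The meaning of disease progression.** Sections 13.1.1.1 and 13.1.8 say that controls will be chosen on the trial's eligibility criteria where possible, and those are baseline data. Progression may therefore have been meant as disease stage. A reader might infer that controls are definitely selected on outcome, or that such selection would hide a true effect by a calculable amount. Neither follows. The wording is ambiguous, and because the reference group mixes both arms, the direction of any bias cannot be derived. Nor can this harm simply be added to the first: controls truly matched on progression would tend to shrink the residual difference assumed above.

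**The weight given to the registries.** The 0.851 is an unstratified share. Stratification by propensity quintile would place randomized placebo in the same strata as OCA, so the registries' effective weight may be lower. This stands, and it is one reason why the figures are illustrative.

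**The no-bias sentence.** It follows a remark about the propensity model only, and 13.1.8 elsewhere concedes that results are conditional on observed covariates. That concession is why the sentence cannot stand as written.

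**Conclusion.** The point holds and should be corrected. Section 13.1.9, if used, gives up an available randomized comparison, conflicts with 5.5.2.3 and leaves the error rate of the primary test dependent on a quantity that cannot be measured. The 17% to 24% is an illustration that rests on the assumed counts and a 20% residual hazard difference. It should not be read as the trial's error rate: with no residual difference the error stays nominal, and with a healthier registry population it turns against OCA. The selection wording in 13.1.1 needs clarifying because one natural reading selects on the outcome, although that reading is not established. The assurance in 13.1.8 is untrue as worded, since leaving outcomes out of the score does not remove unmeasured confounding. The issue arises only if the switch is triggered, except for the wording in 13.1.1 and 13.1.8, which also affects the planned supportive analyses.

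**What to change.** 1. In 13.1.9, keep the stratified log-rank test of randomized OCA against randomized placebo as the primary test, on the composite in 13.1.3, with transplant or death remaining a key secondary endpoint. State that only events in randomized subjects count toward the 121. Give the power at the composite events reached (72% at 100, 63% at 80, for HR 0.60). Report comparisons involving registry controls and open-label OCA separately as supportive, in line with 5.5.2.3.
2. In all three historical control definitions in 13.1.1, replace *disease progression* with *disease stage at the index date*, so that selection uses pre-index data only.
3. In 13.1.8, replace the assurance of no bias with a statement that the results are conditional on the measured covariates.

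The cost is protocol wording, carried through to the SAP. The real downside is power below 80% if fewer than 121 events accrue in randomized subjects, and open-label subjects would contribute only to supportive analyses.
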